4.2.2 Rationale for the Use of Placebo

The primary goal of the study is to evaluate the safety and tolerability of MK-2060 in older adult participants with ESRD on HD. A placebo-controlled study will allow for an unbiased assessment of safety and tolerability of MK-2060, including local infusion site reactions. Secondary and exploratory outcomes are also supported by the use of placebo, including evaluation of the effect of MK-2060 on aPTT following single and multiple dose IV administration, which should only be observed in participants with active treatment.

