Individual aPTT fold-change from baseline values will be natural log-transformed and evaluated with a linear mixed effects model containing fixed effects for treatment and time and treatment by time interaction and random effect for participant. Least squares means and 95% confidence intervals for each treatment, and for the between-treatment differences (MK-2060 – placebo) and 90% CI at each dose level, will be obtained by time. These estimates will be back-transformed to obtain GM aPTT fold-change from baseline by treatment and time and the GMR (MK-2060 fold-change from baseline/placebo fold-change from baseline) by dose and time.

The posterior probability that the true fold-increase from baseline in aPTT 168 hours after a single dose is at least 1.5 will be calculated for each dose assuming normality and using a non-informative (Jeffrey's) prior. A 60% posterior probability for at least one dose level that also exhibits an acceptable safety profile will satisfy the secondary pharmacodynamics hypothesis. In addition, the proportion of subjects with a fold-increase in aPTT 168 hours after a single dose of at least 1.5 will be tabulated.

FXI activity levels, FGA and PT will be evaluated in a similar fashion. Additional model-based analysis may be employed to further explore PD endpoints over time.

Descriptive statistics will be provided for PD endpoints by treatment and time.

Part 2:

As in Part 1, individual aPTT fold-change from baseline values will be natural log-transformed and evaluated with a linear mixed effects model incorporating the longitudinal effects of measurements at the three weekly time points. An unstructured covariance matrix will be used to model the correlation between different measurements within the same subjects. Kenward and Roger's method will be used to calculate the denominator degrees of freedom for the fixed effects. Least squares mean and 95% confidence intervals for each treatment, and for the between-treatment differences (MK-2060 – placebo) and 90% CI will be obtained. These estimates will be back-transformed to obtain GM aPTT fold-change from baseline by treatment and time and the GMR (MK-2060 fold-change from baseline/placebo fold-change from baseline) by time.

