The posterior probability that the true fold-increase from baseline in aPTT is at least 1.5 will be calculated at each of the three weekly time points assuming normality and using a non-informative prior. A 60% posterior probability for at least one of the three time points that also exhibits an acceptable safety profile will satisfy the secondary pharmacodynamics hypothesis. In addition, the proportion of subjects with at least 1.5 fold increase in aPTT 168 hours after the last dose will be tabulated.

FXI activity levels, FGA and PT will be evaluated in a similar fashion. Additional model-based analysis may be employed to further explore PD endpoints over time.

Descriptive statistics will be provided for PD endpoints by treatment and time.

PK-PD

The relationship between plasma concentrations and aPTT, FXI activity, FGA, and PT will be explored graphically. Upon visual inspection, additional model-based analysis may be employed to further explore the PK/PD relationship.

General

For all analyses, data will be examined for departures from the assumptions of the statistical model(s) as appropriate; e.g., heteroscedasticity, nonnormality of the error terms.

Distribution-free methods may be used if a serious departure from the assumptions of the models(s) is observed, or suitable data transformations may be applied.

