If the true CV is 30%, there is approximately 72.3% probability of yielding at least 60% posterior probability that the true fold increase is at least 1.5 if the true fold increase in aPTT after 168 hours of a single well-tolerated subcutaneous dose relative to placebo is at least 1.5. The total participants per dose is 8 (active = 6, placebo = 2).

Part 2:

If the true CV is 30%, for a total of approximately 20 participants (active = 15, placebo = 5), there is approximately 84% probability of yielding at least 60% posterior probability that the true fold increase is at least 1.5. We assume that the true fold increase in aPTT after 168 hours of a single well-tolerated subcutaneous dose relative to placebo is at least 1.5.

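### Section 9.9 gives its aPTT success probabilities for a fold increase relative to placebo, but the 9.6 rule judges fold increase from baseline; the figures cannot describe both

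*Combined protocol and SAP*

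**What the plan says.** **The rule (9.6, Pharmacodynamics).** For Part 1, "The posterior probability that the true fold-increase from baseline in aPTT 168 hours after a single dose is at least 1.5" is the quantity judged, and it "will be calculated for each dose assuming normality and using a non-informative (Jeffrey's) prior". Then: "A 60% posterior probability for at least one dose level that also exhibits an acceptable safety profile will satisfy the secondary pharmacodynamics hypothesis". For Part 2, "The posterior probability that the true fold-increase from baseline in aPTT is at least 1.5 will be calculated at each" of three weekly time points, and the condition is "A 60% posterior probability for at least one of the three time points that also exhibits an acceptable safety profile". Neither rule contains a placebo term. The same section estimates the MK-2060/placebo geometric mean ratio (GMR) of fold changes with a 90% CI, but attaches no criterion to it.

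**The hypotheses.** The synopsis and Section 3 state both aPTT hypotheses, one per part and both secondary, as fold increase from baseline. Section 9.3 restates them without naming the reference. Section 9.4 supplies it: the PD variable is change from the pre-dose baseline.

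**The sizing (9.9, Pharmacodynamics).** At a true CV of 30%, 9.9 states about 72.3% probability of reaching a 60% posterior in Part 1 (6 active, 2 placebo per dose) and about 84% in Part 2 (15 active, 5 placebo). In both parts the true effect is the fold increase after a "single well-tolerated subcutaneous dose relative to placebo is at least 1.5". No other true value is given.

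**The role of placebo (4.2.2).** "Secondary and exploratory outcomes are also supported by the use of placebo, including evaluation of the effect of MK-2060 on aPTT". The sentence goes on to say that this effect is expected only on active treatment.

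**The concern.** A stated probability of success is useful only if it belongs to the rule that will be applied. Here the rule is a within-arm comparison with baseline, while the sizing text describes a between-arm effect and counts the placebo participants. The two differ in precision, because a placebo-relative estimate also carries the error of a small placebo mean. They also differ in meaning: a change shared by both arms moves the from-baseline estimate and cancels from the ratio.

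A reader of 9.9 therefore cannot tell what the 72.3% and 84% refer to, or which true fold lies behind them. The protocol says that trial data will help dose selection (2.1), so the operating characteristics of its only formal hypotheses should be traceable.

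**Working it through.** **Inputs.** CV 30%, arm sizes, the 1.5 threshold and the 60% criterion come from 9.6 and 9.9. Assumptions of this check: the CV applies to each participant's log fold change; the arms have equal variance; the prior is Jeffreys; the calculation is for one dose or one time point.

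**Formulas.**
- Log SD: s = √ln(1 + 0.30²) = 0.2936.
- Standard error: s√(1/n) from baseline; s√(1/nA + 1/nP) relative to placebo.
- With a Jeffreys prior the posterior is t-shaped, so the rule is met when ln(observed fold / 1.5) / SE is at least t(0.60, df).
- The success probability is a noncentral t tail with noncentrality ln(true fold / 1.5) / SE.

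| Comparison | SE | df | Observed fold needed |
|---|---|---|---|
| Part 1, from baseline, n = 6 | 0.120 | 5 | 1.55 |
| Part 1, 6 v 2 | 0.240 | 6 | 1.60 |
| Part 1, 6 v 6 (placebo pooled over panels) | 0.170 | 10 | 1.57 |
| Part 2, from baseline, n = 15 | 0.076 | 14 | 1.53 |
| Part 2, 15 v 5 | 0.152 | 18 | 1.56 |

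**Step 1: the plan's own figures.** At a true fold of exactly 1.5 the noncentrality is zero, so success is 1 − 0.60 = 40% for every row, whatever the sample size or CV. Neither 72.3% nor 84% is reproduced. Any-of-three success at 1.5 is 1 − 0.60³ = 78.4% for independent looks, 71.9% at correlation 0.25 and 65% at correlation 0.5. The second of these is close to 72.3%, but no such reading gives both figures, and 9.9 describes Part 1 per dose.

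**Step 2: back-solve the true fold.** Both figures return only with a fold that the documents do not state. The table applies each rule at the fold that reproduces the plan's figure under the other.

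| Figure taken as | Fold that gives it | Other rule at that fold |
|---|---|---|
| 72.3%, from baseline, n = 6 | 1.66 | 56.7% (6 v 2); 63.5% (6 v 6) |
| 84%, from baseline, n = 15 | 1.65 | 64.5% (15 v 5) |
| 72.3%, relative to placebo, 6 v 2 | 1.84 | 92.4% (n = 6) |
| 72.3%, relative to placebo, 6 v 6 | 1.73 | 82.6% (n = 6) |
| 84%, relative to placebo, 15 v 5 | 1.81 | 98.8% (n = 15) |

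A common fold near 1.65 fits both figures within 2 points from baseline (70.5% and 84.2%). A common fold near 1.82 does so relative to placebo (70.9% for 6 v 2, 84.6% for 15 v 5). The figures therefore cannot show which estimand was sized.

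**Step 3: sensitivity to the SD.** If the log SD is multiplied by √2, the 40% at 1.5 is unchanged. At a fold of 1.65 (normal approximation), Part 1 gives 62% from baseline against 51% (6 v 2) or 56% (6 v 6). Part 2 gives 74% against 58%.

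**Step 4: what a shared change would do.** The documents report no drift; these values are assumed. With a true MK-2060/placebo ratio of 1.4:

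| Shared change | From baseline, n = 6 | From baseline, n = 15 |
|---|---|---|
| None | 20% | 12% |
| +5% | 34% | 30% |
| +10% | 49% | 54% |

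A rule on the ratio gives 29% (6 v 2), 25% (6 v 6) and 24% (15 v 5) at any drift. In the other direction, with a true ratio of 1.5 and placebo falling 10%, the from-baseline rule passes 13% (n = 6) and 5% (n = 15), against 40% for the ratio.

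**The case against.** A reader might infer that the decision rule itself is faulty: that it is a before-and-after test that ignores the randomised control and must be replaced. The documents do not support that, for five reasons.

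- **The rule tests the hypothesis as written.** The synopsis, Section 3 and the 9.4 endpoint are all from baseline, and 4.3.4 expresses its trough aPTT projection against baseline. Section 9.9 is the outlier. It also refers to a subcutaneous dose in an IV trial and to a single dose for Part 2, which suggests carried-over wording.
- **The no-placebo-change assumption is stated and can be checked.** Section 4.2.2 expects the aPTT effect only on active treatment, and 9.6 reports the GMR with its 90% CI.
- **No drift is documented, and design features limit it.** The analysed aPTT is central-lab (8.9.1), pre-dose samples precede dialysis (1.3), 6.6.1 gives heparin a half-life of about 1 hour, and the 168-hour samples fall whole weeks after Day 1.
- **A placebo-relative rule is not uniformly stricter.** With no drift it passes a true 1.4-fold dose more often: 25–29% against 20% in Part 1, and 24% against 12% in Part 2. Its standard error is double at 6 v 2 and at 15 v 5.
- **At the plan's own projection the choice matters less.** Section 4.3.3 predicts about 2-fold at 168 hours for 40 mg. There the from-baseline rule passes 98%, and the ratio rule 93% (6 v 6) or 83% (6 v 2).

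All of this stands against replacing the rule. It does not remove the mismatch with 9.9 or supply the missing true fold. Nor is a shared change ruled out: Day 8 has both pre- and post-dialysis PD draws (1.3.1), and 9.6 does not say which one enters the rule. It would also be too strong to say that placebo has no influence on the decision. Placebo data could inform a pooled model variance, and the rule also requires an acceptable safety profile.

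**Conclusion.** The point holds as a mismatch between 9.6 and 9.9. The rule and the hypotheses concern fold increase from baseline. The stated probabilities are attached to a fold increase relative to placebo, and one pair of figures cannot serve both. At the back-solved folds the gap is 9 to 16 points in Part 1 (72.3% against 63.5% or 56.7%) and about 20 points in Part 2 (84% against 64.5%). These sizes rest on CV 30% for the individual log fold change, a Jeffreys prior and a single dose or time point. The folds of about 1.66 and 1.65 are inferred and appear nowhere in the documents.

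The finding that does not depend on them is the 40% at a true fold of exactly 1.5, under either rule. Since 9.9 says at least 1.5, its figures must belong to some larger, unstated value.

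The drift figures show why a placebo-relative posterior is worth seeing. They are not evidence that drift occurs.

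**What to change.** 1. **In 9.9**, name the estimand that the 9.6 rule uses. That is from baseline, unless the sponsor chooses to move the hypothesis to the MK-2060/placebo GMR throughout. Restate the Part 1 and Part 2 probabilities for that rule at an explicit assumed true fold, and say whether each is for one dose or time point or for any of three.
2. **In 9.6**, for both parts, also report the posterior probability that the MK-2060/placebo GMR at 168 hours is at least 1.5 (after the last dose in Part 2). Place it beside the from-baseline posterior as a supporting figure, so that a change shared by both arms is seen before the hypothesis is declared satisfied. State whether Part 1 placebo is pooled over panels.

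The cost is revised wording, one extra posterior on a contrast the model already produces, and possibly a less favourable stated probability. Making the GMR the sole criterion is not required. It would trade protection against a shared change for a doubled standard error at 6 v 2 or 15 v 5. It would also mean amending the hypotheses and endpoint in 1.1, 3, 4.2.1.3, 9.3 and 9.4.

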12-lead electrocardiogram	X		X	X	X	X	X	X	X	X	X	X	X		X					X	Sec. 8.3.3. Predose and 3.5 hrs postdose on each dosing days	
Laboratory Procedures/Assessments																						
Safety Lab	Hematology and Chemistry	X	X	X		X		X	X	X	X	X	X		X		X	X	X	X	Sec. 8.4.3, 10.2 (Appendix 2) and 10.9 (Appendix 9).	
	aPTT/PT at Local Lab	X		X(3)		X(2)	X(2)	X(2)	X	X(2)	X	X(2)	X	X	X	X	X	X	X	X	Day 1: Predose, 1 and 12 hrs postdose. Predose may be performed within 3 days of dosing. Days 3, 5, 8, 15 and 22: 1 and 12 hrs postdose.	
	Hemoccult Test		X		X		X	X	X	X	X	X	X		X	X	X	X	X	X	Sec. 8.4.3, 8.11.6, 10.2 (Appendix 2) and 10.9 (Appendix 9).	
	HIV/hepatitis Screen	X																			Per site SOP	
	Serum/saliva Drug and Alcohol Breath Test	X	X	X																	Per site SOP	
	Serum Follicle Stimulating Hormone (FSH)	X																			Postmeno-pausal/oophorectomized female participants only	
	Serum β-Human Chorionic Gonadotropin (β-hCG)	X																		X	Female participants only	
	AE/SAE review	X																		X	Sec. 8.5 and 10.3 (Appendix 3)	

Study Period	Screening ≤28 days to Day 1	Intervention																		Post- study	Notes		
		Week 1		Week 2		Week 3		Week 4		Post Week 4													
Scheduled Week/Day	Scn1	Scn2 ^d	1	2	3	5	8	10	15	17	22	23	24	26	29	35	42	49	63	81	111	Sec. 8.11 for Visit Requirements and Sec. 8.11.6 for Timing of Procedure	
			NA	NA	NA	NA	NA	±1	NA	±1	NA	NA	NA	+1	NA	±2	±2	±2	±3	±3			
Pharmacokinetics																							
Blood for Plasma MK-2060 Assay			X(3)	X	X(2)	X(2)	X(2)	X	X(2)	X	X(3)	X	X	X	X	X	X	X	X	X	Sec. 8.7 Days 1 & 22: predose, 1h (within 5 min end of infusion), 12h. Days 3, 5, 8 & 15: predose, 1h (end of infusion). See footnote e, f.		
Pharmacodynamics																							
Blood for PT/aPTT/ FXI Activity by Central Lab			X(2)	X	X	X	X	X	X	X(2)	X	X	X	X	X	X	X	X	X	X	Sec. 8.8, Days 1 and 22 (2 draws): predose and 1h (within 5 min end of infusion).		
Blood for Fibrin Generation Assay			X(2)	X	X	X	X	X	X	X(2)	X	X	X	X	X	X	X	X	X	X			
Blood for biomarker(s) of inflammation (e.g., hsCRP) Assay			X				X		X		X				X	X	X	X	X	X			
Biomarkers																							
Blood for plasma anti-drug antibody			X							X		X						X	X	X	X	See Section 8.9 On dosing Days 1, 15, and 22: draw sample at predose.	
Blood for Genetic Analysis			X																			See footnote c.	
5-D Pruritus Scale												X				X							

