4.3.4 Rationale for Multiple Dose Regimen (Part 2)

The primary intent of Part 2 is to evaluate the safety, tolerability, PK, and PD of an MK-2060 multiple dose regimen that will achieve target anticoagulation. For anticoagulants, it is desirable to achieve near target anticoagulation as soon as therapy is initiated so a loading dose is being used for this portion of the study. 40 mg IV is the highest dose assessed in PN001 in NHVs and in ESRD patients in Part 1 of PN004. In PN001 with a single 40 mg IV dose Cmax and AUC_{0-168hr} the geometric mean (GCV) were 78.2 (11.8) nM and 6350 (17.6) nM*hr, respectively. Preliminary dose modelling based on PK/PD data from the available 8, 20, and 40 mg single dose data in ESRD patients in Part 1 of PN004 projects that a regimen of 25 mg dosed on Days 1, 3, and 5 followed by 3 maintenance doses of 25 mg QW is projected to have a median Cmax (post first maintenance dose) of 91 nM and AUC_{0-168hr} (post last dose) of 8868 nM*hr. From a safety perspective, the steady state Cmax of the 25 mg IV QW dose is projected to be \sim 25% higher than the Cmax achieved with the 40 mg IV single dose in PN001. Due to the slight increase in projected steady state Cmax in Part 2, the domiciling period has been increased during the first week of dosing for additional safety monitoring. As discussed above, all doses of MK-2060 have been generally well tolerated with no dose related SAEs, discontinuations due to AEs, or AEs suggestive of hypersensitivity, therefore no safety issues are anticipated in Part 2 with this slightly higher exposure. 25 mg QW is projected to result in $>90\%$ of participants with aPTT of 1.5 fold baseline at trough. The multiple dose regimen of Part 2 (3 doses for week 1 plus 3 maintenance doses) steady state is projected to be achieved by end of week 1 (concentration \sim 90% of steady state).

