5.2 Exclusion Criteria

The participant must be excluded from the study if the participant:

Medical Conditions

1. Has a history of any clinically significant concomitant disease or condition (including treatment for such conditions) or diseases whose current condition is considered clinically unstable that, in the opinion of the investigator, could either interfere with the study drug, compromise interpretation of study data, or pose an unacceptable risk to the patient. Participants with a remote history of uncomplicated medical events (e.g., uncomplicated kidney stones, as defined as spontaneous passage and no recurrence in the last 5 years, or childhood asthma) may be enrolled in the study at the discretion of the investigator.

2. Is mentally or legally incapacitated, has significant emotional problems at the time of pre-study (screening) visit or expected during the conduct of the study or has a history of clinically significant psychiatric disorder of the last 5 years. Participants who have had situational depression may be enrolled in the study at the discretion of the investigator.
3. Has a history of cancer (malignancy), including adenocarcinoma,

Exceptions: (1) Subjects with adequately treated non-melanomatous skin carcinoma may participate in the trial; (2) Subjects with other malignancies which have been successfully treated ≥ 10 years prior to the pretrial (screening) visit where, in the judgment of both the investigator and treating physician, appropriate follow-up has revealed no evidence of recurrence from the time of treatment through the time of the pretrial (screening) visit (except those cancers identified at the beginning of exclusion criterion 10); or, (3) Subjects, who, in the opinion of the trial investigator, are highly unlikely to sustain a recurrence for the duration of the trial.

4. Has blood coagulation test (aPTT, PT) $\geq 20\%$ outside of normal range on pretrial (screening), which are considered clinically significant by both the investigator and the sponsor.
5. Any other clinically significant abnormalities in laboratory test results at screening that would, in the opinion of the investigator, increase the patient's risk of participation, jeopardize complete participation in the study, or compromise interpretation of study data.

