8.9.1 Blood Collection for PT, aPTT, FXI Activity and FGA Assay

Part 1: PT and aPTT at screening, 1 hour, 12 hour, 48 hours, Day 5, Day 8, Day 12, Day 15, Day 22, and Day 90 post-dose will be performed locally for safety monitoring. All other pre-dose and post-dose PT and aPTT, as well as FXI activity will be performed at a central vendor for PK/PD analysis. FGA assays will be performed by the Sponsor. Sample collection, storage, and shipment instructions for the PT, aPTT, FXI activity, and FGA assays will be provided in a separate trial Study Operations Manual by the Sponsor. The primary data for statistical analysis and modeling will be based on the information from the central vendor.

Part 2: PT and aPTT at screening, predose, 1 hour, 12 hour postdose on each dosing day (Days 1, 3, 5, 8, 15 and 22), Day 10, Day 17, Day 23, Day 24, Day 26, Day 29, Day 35, Day 42, and Day 111 post-dose will be performed locally for safety monitoring. All other pre-dose and post-dose PT and aPTT, as well as FXI activity will be performed at a central vendor for PK/PD analysis. FGA assays will be performed by the Sponsor. Sample collection, storage, and shipment instructions for the PT, aPTT, FXI activity, and FGA assays will be provided in a separate trial Study Operations Manual by the Sponsor. The primary data for statistical analysis and modeling will be based on the information from the central vendor.

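### Should the Part 2 aPTT model have carried baseline aPTT as a covariate for the MK-2060/placebo ratio?

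*Combined protocol and SAP*

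**What the plan says.** Section 9.6 (Pharmacodynamics, Part 2) follows Part 1, with fold changes "natural log-transformed and evaluated with a linear mixed effects model incorporating the longitudinal effects of measurements at the three weekly time points". Covariance within a participant is left unstructured, and degrees of freedom follow Kenward-Roger. The Part 1 model that it follows is "evaluated with a linear mixed effects model containing fixed effects for treatment and time and treatment by time interaction and random effect for participant". Neither list contains baseline aPTT. Baseline enters only as the denominator of the fold change; section 9.4 defines it as the panel-specific pre-dose value.

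One planned output is "the GMR (MK-2060 fold-change from baseline/placebo fold-change from baseline) by time", with a 90% confidence interval. The secondary hypothesis is decided by a different quantity, the posterior for the fold increase from baseline: "A 60% posterior probability for at least one of the three time points that also exhibits an acceptable safety profile" satisfies it.

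The covariate would be available. The Part 2 schedule (section 1.3.2) lists central-laboratory draws on "Days 1 and 22 (2 draws): predose and 1h (within 5 min end of infusion", and section 8.9.1 states: "The primary data for statistical analysis and modeling will be based on the information from the central vendor".

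**The concern.** Baseline adjustment of a change score is commonly recommended. A log fold change assumes that post-dose ln aPTT rises one for one with baseline ln aPTT. If the true slope differs from 1, a chance baseline difference between the arms stays in the ratio, and with about 5 placebo participants such differences can be sizeable. Section 9.6 does name covariates elsewhere (sex and age in the Part 1 PK model), so their absence here stands out. The baseline sample is drawn anyway. At stake would be the width of the 90% interval for the MK-2060/placebo ratio, and some protection of its point estimate against chance imbalance.

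**Working it through.** The plan states no expected width for this ratio, so there is none to reproduce. The 84% in section 9.9 concerns the posterior rule and does not enter.

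**Inputs.** From section 9.9: 15 active, 5 placebo, CV 30%, read here as the CV of the fold change. Assumed, because the documents are silent: baseline log SD, and the slope β of ln post-dose aPTT on ln baseline. The calculation is for one time point; with complete data, treatment-by-time terms and unstructured covariance, the contrast at each time is the difference in that time's means.

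**Planned interval.**
- Log SD = √ln(1 + 0.30²) = 0.2936.
- SE = 0.2936 × √(1/15 + 1/5) = 0.2936 × 0.5164 = 0.1516.
- Half-width = t(0.95, 18) × SE = 1.734 × 0.1516 = 0.263, so the limits are the observed ratio ×/÷ 1.30.

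**Effect of the covariate, common slope and variance.** The log fold change has slope β − 1 on ln baseline. Its within-arm correlation with ln baseline is r = (β − 1) × SD_base / 0.2936. The covariate removes a share r² of the variance, but costs one degree of freedom (t ratio 1.003) and the expected imbalance term √(1 + 1/16) = 1.031:

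width ratio ≈ 1.003 × 1.031 × √(1 − r²) = 1.034 × √(1 − r²).

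Break-even is at |r| of about 0.25; below that the adjusted interval is wider on average. Example: β = 0.5, SD_base = 0.15 gives r = −0.5 × 0.15 / 0.2936 = −0.255 and a ratio of 1.00.

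| Baseline log SD | β = 0.3 | β = 0.5 | β = 0.7 | β = 0.9 |
|---|---|---|---|---|
| 0.10 | 1.00 | 1.02 | 1.03 | 1.03 |
| 0.15 | 0.97 | 1.00 | 1.02 | 1.03 |
| 0.20 | 0.91 | 0.97 | 1.01 | 1.03 |

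Simulation agrees to within 0.01 in every cell, with coverage about 0.90 for both models. Only three cells gain more than 1%. In the best, the multiplier falls from 1.30 to exp(0.909 × 0.263) = 1.27; in the worst it rises to 1.31.

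**Where larger gains come from.** At |r| = 0.5 and 0.6 the ratio is 0.89 and 0.83. Assuming equal log SDs at baseline and post-dose, with correlations of 0.5 and 0.3, gives the same figures. At a correlation of 0.3 that assumption needs a baseline log SD of 0.2936 / √(2 × 0.7) = 0.25, so ±2 SD spans a factor of exp(4 × 0.25) = 2.7. Exclusion criterion 4 bars aPTT or PT at least 20% "outside of normal range on pretrial (screening), which are considered clinically significant by both the investigator and the sponsor". That is a loose limit, but a spread this wide is hard to count on.

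**Chance imbalance.** A one-SE baseline difference moves the planned ratio by exp(|r| × 0.1516) − 1: 3.9% at |r| = 0.25 and 7.9% at 0.5. The ratio's own SE is exp(0.1516) − 1 = 16%, and that already includes this component.

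**Unequal slopes.** With an active slope of 1.5, placebo slopes of 0.3 to 0.9, the same baseline SDs and equal fold-change variances, the adjusted log ratio has a true SD about 4% to 9% larger than the planned one. Coverage falls to as little as about 0.88. A steeper active slope is plausible: placebo values reflect retest behaviour, active values a drug effect.

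**The case for a change.** The strongest opposing case is that adjustment needs no new data and costs at most about 3% in average width under a common slope and variance, while it could gain 5% to 17% at |r| of 0.4 to 0.6. Deciding before unblinding would also avoid a later choice between two ratios. The text supports the factual part: no baseline covariate is named, and the clause in section 9.6 allowing additional model-based PD analyses does not prespecify one.

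The cost figure, however, holds only when the slopes are equal. A slope comparison in Part 1 has been suggested as a safeguard, but it would rest on 18 active and 6 placebo participants. For an active slope of 1.5 against placebo slopes of 0.3 to 0.9, its power at the two-sided 5% level is about 7% to 32%, so it would usually miss the case it is meant to catch. Access is also uncertain. Section 4.3.4 refers to "Preliminary dose modelling based on PK/PD data from the available 8, 20, and 40 mg single dose data in ESRD patients" without mentioning placebo, and section 9.7 limits in-life summaries for dose escalation to blinded aggregates without individual results.

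One could add that section 9.9 words the assumed effect as relative to placebo, which might bring the ratio into the decision. Sections 9.3 and 9.6 define the hypothesis and rule by the fold increase itself, and section 9.6 specifies from baseline. Even on the other reading, the covariate would act through the same modest change in precision. FXI activity, FGA and PT are to be evaluated similarly, and the reasoning is the same for them.

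**Conclusion.** The concern does not hold. Baseline is already in the response, omitting the covariate causes no bias, the planned 90% interval has its nominal coverage under a common slope and variance, and the 60% rule as section 9.6 states it does not use the ratio. The effect of adjustment runs from 9% narrower to 3% wider over the assumed common slopes and baseline spreads, mostly with no gain, and it can be harmful if the arms' slopes differ. With about 5 placebo participants, the usual argument that baseline adjustment is nearly free does not carry over.

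This rests on the 30% CV being that of the fold change, on the assumed slopes and baseline log SDs, and on one time point with complete data. A true baseline log SD well above 0.20 with a common slope far from 1 would make adjustment more worthwhile, but nothing in the documents shows this. An adjusted ratio may still be shown as a sensitivity analysis under the plan's existing allowance for further PD modelling; that is a matter of preference, and its absence is not a fault.
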